4. STUDY PROCEDURES

Study procedures are described as follows and depicted graphically in [Section 4.3](#), below. Acceptable deviations from the visit schedule are indicated. These variations must not be cumulative; i.e. visits should always be scheduled in relationship to Visit 1 (Day 0).

4.1. Visit 1 (Day 0)

At the screening visit, the following procedures will be undertaken:

- Subject is fully informed about the study and gives written agreement to study participation in the form of a signed informed consent form (refer to [Section 4.1.1](#))
- Assess eligibility (refer to [inclusion/exclusion criteria](#))
- Review of medications
- Medical history including history of constipation (ROME criteria – See [Inclusion #2](#))
- Physical examination
- Vital signs, including assessment of orthostatic hypotension (while seated and after standing for a minimum of 2 minutes) including height and bodyweight, pulse and temperature
- A 12-lead ECG will be performed by qualified, trained site personnel. ECG output must be reviewed by a physician investigator. Any clinically significant cardiac abnormalities identified on the ECG should disqualify a subject. Data from the ECG will be collected in the eCRF.
- Urine pregnancy test (if applicable)
- Blood and urine samples will be collected for testing at a central laboratory, as shown below.

Chemistry: alkaline phosphatase, ALT, anion gap, AST, bicarbonate, blood urea nitrogen (BUN), calcium, chloride, creatine kinase, creatinine, eGFR, GGT, HCG, inorganic phosphate, magnesium, osmolality, potassium, sodium, uric acid. CK-MB will be tested in samples where the CK value is greater than 2.5 times the upper normal limit.

Hematology: hematocrit, hemoglobin, platelets count, red blood cell count, white blood cell count (and differentials)

Urinalysis: including electrolytes (sodium, potassium, magnesium, calcium), microscopic analysis, urine osmolality

Subjects with clinically significant laboratory abnormalities, deemed as a potential safety issue by the Investigator, may be discontinued at the Investigator's discretion.

If the subject is eligible for the study, assign a subject number.

Braintree Laboratories, Inc.
Protocol Number BLI400-303

Confidential

- Subjects will complete the Patient Assessment of Constipation Quality of Life questionnaire (PAC-QOL, refer to [Appendix A](#)) and the Patient Assessment of Constipation Symptom questionnaire (PAC-SYM, refer to [Appendix B](#))
- Dispense 2 bottles of BLI400
- Dispense rescue bisacodyl. Subjects will be allowed to take 5 – 10mg of bisacodyl if they are experiencing severe discomfort due to their constipation, or have not had a BM in 4 days.
- Instruct subject to maintain their normal dietary habits during study participation
- Schedule the next study visit to occur after 60 days

Subjects that are ineligible due to prohibited medication use (Exclusion Criterion 10) may be washed out for a period of 14 days. No additional procedures should be performed on these subjects. After the washout period, subjects may be enrolled and all Visit 1 procedures should be repeated (with the exception of obtaining informed consent).

4.1.1. **Informed Consent**

Following the informed consent process, study subjects will sign a current IRB approved consent form. No study procedures may be performed prior to the subject providing informed consent. The subject's original signed and personally dated Informed Consent Form (together with any subsequent IRB approved amended versions) must be retained by the Investigator in the subject's file. A copy of the original signed and dated Informed Consent Form must be given to the subject.

4.1.2. **Enrollment and Allocation of Subject Number**

Subjects will be enrolled into the study only when they have given their written, informed consent to participate.

Subjects enrolled at the screening visit will be assigned a subject number by site personnel.

This number will consist of:

- The 3-digit Site Number;
- The 3-digit subject identifier number (this number is a sequentially allocated number). Each site will begin with 001 for the first subject screened, 002 for the second and so on. For example, the third subject screened at Site 15 will become Subject Number 15-003. After a subject completes all screening procedures and eligibility has been confirmed, site personnel will assign a subject number.

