1. INTRODUCTION

The present approaches to the treatment of chronic idiopathic constipation (CIC) are limited and for some patients there are significant drawbacks that have not been resolved. It would be desirable to provide a source of relief for constipation that would permit dosing adjustments to optimize efficacy and safety and that would be pleasant to consume to improve patient compliance. The treatment should not have the safety issues associated with oral phosphate laxatives, have an acceptable safety profile, and be effective in numerous types of constipation.

Braintree Laboratories, Inc. is investigating the use of a new chemical composition, BLI400 (Lactitol Monohydrate NF Powder for Reconstitution) as a treatment for adult constipation. Ample published literature with lactitol provides significant preclinical and clinical studies which support the safe and effective use of this GRAS-listed compound.

These reports indicate that the BLI400 lactitol composition has promise as a candidate for further development for the treatment of constipation, as reviewed herein.

BLI400 is a member of the pharmaceutical class of osmotic laxatives; specifically it is a non-absorbed, colonically metabolized sugar alcohol (polyol). Studies reviewed here indicate it provides relief from the symptoms of constipation by rapidly inducing a patient-controlled bowel movement. While lactitol appears to be minimally, if at all, absorbed in the small intestine, colonic microbes split lactitol into D-galactose and D-sorbitol, which are fermentable to organic acids including lactic, formic, propionic, butyric and acetic acids (as reviewed in [Patil et al, 1987](#)). The osmotic properties of the small organic molecules consistently point to their pharmacodynamic effects as dependent on water retention with the stool. Thus, BLI400 is a pro-drug of an essentially non-absorbed osmotic laxative. Lactitol is generally considered to be pharmacologically inert and is often referred to as a “prebiotic” with no specific receptor targets for its laxative action.

Rationale for Performing Research with the Investigational Product

Lactitol monohydrate, at a daily dose of 21 grams per day appears to be a safe and effective treatment for constipation, but it has not been studied and proven in clinical

Braintree Laboratories, Inc.
Protocol Number BLI400-303

[figure not shown]
Confidential

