Metabolic Effects: In some studies, total serum cholesterol and triglycerides were reduced equally in rats fed diets containing 7% sorbitol or lactitol. By acidifying fecal contents, lactitol lowered ammonia levels in animal models of hepatic encephalopathy, perhaps as a result of production of the poorly absorbed ammonium ion that follows lowering the cecal pH. Rats fed a diet containing 5% of lactitol for two weeks displayed a significant increase of calcium absorption.

Toxicology Studies: Only weak edema ensued after lactitol application to intact skin, but erythema and edema emerged when it was applied to abraded skin. Rodents treated with lactitol had loose, frequent stools and cecal enlargement. This was often accompanied by decreased weight gain and increased water consumption. Clinical chemistry changes included changes in electrolyte levels, decreased cholesterol and alkaline phosphatase. Perhaps as compensation for the electrolyte changes that probably followed the diarrhea, adrenal weight and hypertrophy of the zona fasciculata were seen in the highest dose groups. Renal tubular degeneration with nephrocalcinosis was occasionally seen and may follow the increased calcium absorption. Lactitol was not considered positive for mutagenicity or chromosomal damage studied in standard in vitro and in vivo assays. Life-long carcinogenicity studies have indicated that Leydig cell dysplasia occurred in

rats at high lactitol doses, but this was not seen in mice dosed for 24 months or dogs dosed for 12 months. This species-specific effect in some rat strains was not considered significant to humans, since ordinary milk sugar, lactose, produces a similar effect in rodents.

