4.2.2. Visit 2 (*Month 2*) +/- 4 days

Subjects will continue to take BLI400 daily and will return to the clinic for Visit 2 (Day 60). Vital signs (see [section 4.1](#) for details) and ECGs will be recorded. Study personnel will weigh returned bottles and count rescue bisacodyl for accountability purposes. Subjects will be queried for any adverse events or changes to their concomitant medications. Subjects will complete the PAC-QOL and PAC-SYM questionnaires. Samples for chemistry, hematology and urinalysis will be repeated as outlined in [Section 4.1](#). Subjects will be dispensed 2 new bottles of study medication. Subjects will be instructed to return all bottles and bisacodyl at the next follow up visit.

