4.3. Tabulated Study Procedures

The following graphically depicts the flow of study procedures at each visit.

Procedures	Visit 1 Day 0	Visit 2 Month 2 +/- 4 days	Visit 3 Month 4 +/- 4 days	Visit 4 Month 6 +/- 4 days	Visit 5 Month 9 +/- 4 days	Visit 6 Month 12/ ET +/- 4 days	☞ Day 374 +/- 4 days
Informed Consent	X						
Inclusion/Exclusion Criteria Review	X						
Medical History	X						
Physical Examination	X					X	
Vital Signs ¹	X	X	X	X	X	X	
Electrocardiogram	X	X				X	
Review of Concomitant Medication	X	X	X	X	X	X	X
Urine Pregnancy Test (if applicable) ²	X						
Enroll Eligible Subjects	X						
Subject to Complete PAC-QOL, PAC-SYM	X	X	X	X	X	X	
Blood Sample for Chemistry Testing	X	X	X	X	X	X	
Blood Sample for Hematology Testing	X	X	X	X	X	X	
Urine Sample for Urinalysis	X	X	X	X	X	X	
Blood Sample for Serum Pregnancy Testing				X		X	
Dispense Study Drug and Rescue Bisacodyl	X	X	X	X	X		
Study Drug and Rescue Bisacodyl Accountability		X	X	X	X	X	
Assess Safety		X	X	X	X	X	X

¹blood pressure and pulse while seated and after standing for 2 minutes, temperature, weight and height (@Visit 1

²only) refer to [Section 4.4](#)

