9.3.2. Safety Analyses

Analysis of safety will be performed using the modified Intent to Treat population (see [Section 9.4](#)).

Adverse Events

Adverse Events will be coded using the MedDRA classification to provide a preferred term and primary system organ class for each event. Proportions of subjects with adverse events will be presented for the overall study population, and each demographic subgroup (age, gender and race). Tables of AEs will be presented by system organ class and preferred term, and include overall totals for AEs within each system organ class. Counting will be done by subject and not by event. A table of counts and percentages will also be made of those subjects with SAEs or AEs which led to withdrawal from the study.

Treatment-emergent AEs are defined as adverse events that had an onset day and time on or after the day and time of the first dose of study drug until the Day 374 Follow-up Call. Adverse Events having missing onset dates will be considered as treatment emergent.

The difference in adverse event rates between study periods will be tested by Chi-Square or Fisher's exact test with 95% confidence intervals.

Laboratory Parameters

Summary statistics (i.e., mean, minimum, maximum, standard deviation, and number of subjects) will be presented for each laboratory parameter at each visit. Laboratory data will be summarized for the overall population and the elderly and non-elderly subgroups. When calculating the summary statistics only, the last observation within a visit window will be used if there are multiple observations. Changes from baseline (Visit 1) will be presented in a similar format. An additional listing will be provided of those subjects who have clinically significant laboratory values. The data will also be presented as shift tables and clinically significant abnormalities will be examined.

Results of laboratory tests for the change from baseline (Visit 1) and group differences will be tested using ANOVA.

Vital Signs

Summary statistics (i.e., mean, minimum, maximum, standard deviation, and number of subjects) will be presented for each vital sign at each visit and compared to the values obtained at Visit 1. When calculating the summary statistics only, the last observation within a visit window will be used if there are multiple observations. The data will also be presented as shift tables and clinically significant abnormalities will be examined.

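### Urine electrolytes are tested as untimed-sample concentrations with no urine creatinine, so a change in urine dilution could pass for, or hide, a change in excretion

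*Combined protocol and SAP*

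**What the plan says.** Section 4.1 states: "Blood and urine samples will be collected for testing at a central laboratory, as shown below". The urine list that follows is "Urinalysis: including electrolytes (sodium, potassium, magnesium, calcium), microscopic analysis, urine osmolality". Creatinine appears only in the blood chemistry list, which includes "chloride, creatine kinase, creatinine, eGFR, GGT, HCG, inorganic phosphate, magnesium, osmolality, potassium, sodium, uric acid" (calcium is named earlier in the same list). No collection period, volume, time of day or fasting condition is given for the urine sample.

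The sampling recurs on treatment. Section 4.2.2 says "Samples for chemistry, hematology and urinalysis will be repeated as outlined in" Section 4.1, and Sections 4.2.3 to 4.2.6 say the same. In Section 4.3 the row "Urine Sample for Urinalysis" is marked at all six clinic visits. The first dose is taken the day after Visit 1 (Section 4.2.1), so the baseline sample precedes study drug.

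Section 9.3.2 has one rule for all laboratory parameters: summary statistics by visit, change from Visit 1, shift tables, and a test. On the test it says: "Results of laboratory tests for the change from baseline (Visit 1) and group differences will be tested using ANOVA". It defines no ratio, covariate or other adjustment for urine concentration, and gives urine osmolality no role in reading the electrolytes. The Clinical Protocol Summary Sheet makes the comparison of urinalysis values with baseline part of the primary endpoint. Section 3.1 describes a study in which every subject receives BLI400. Both copies of the protocol in the file agree on these points.

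**The concern.** Without a volume or a reference solute, a urine electrolyte value from a visit sample is a concentration. It moves when excretion changes, and it also moves when the subject is more or less hydrated. Random differences in dilution only add noise. A shift that affects most subjects between baseline and the treated visits biases the mean change.

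Section 1 gives a reason to consider such a shift for this drug: "The osmotic properties of the small organic molecules consistently point to their pharmacodynamic effects as dependent on water retention with the stool". With one arm, no between-group comparison can separate a hydration effect from a renal effect.

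The analyte for which this matters most is urine calcium. Among the animal findings, Section 1 reports: "Renal tubular degeneration with nephrocalcinosis was occasionally seen and may follow the increased calcium absorption". A calcium concentration that rises because urine is more concentrated could be read as added calcium load. A true rise could go unseen if urine became more dilute.

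**Working it through.** The plan has no figure to reproduce. Section 9.1 takes 300 subjects from an exposure guideline and gives no alpha, power, standard deviation or effect size. What follows illustrates sensitivity and does not predict an effect.

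**Inputs from the documents.** Urine sampled at six visits, one before dosing and five after; up to 300 subjects; change from Visit 1 tested as measured; no urine creatinine or volume listed.

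**Assumptions, not in the documents.** A fall *v* in urine volume of 5% to 30% in all subjects; a standard deviation of the within-subject log change of 0.4 to 0.8; 100 to 300 evaluable subjects; a two-sided 0.05 paired test on the log concentration, standing in for the planned test of change.

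**Step 1: effect on concentration.** Concentration = excretion / volume. With excretion unchanged, a fall *v* multiplies every concentration by 1/(1 − v). For v = 10% this is 1/0.90 = 1.111, or +11.1%. For v = 20% it is 1/0.80 = 1.25, or +25.0%. The direction can reverse: a 10% or 20% rise in volume gives 1/1.10 = 0.909 (−9.1%) or 1/1.20 = 0.833 (−16.7%). With no systematic change the bias is zero.

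**Step 2: chance that the test flags it.** The probability is Φ(ln(ratio)/SE − 1.96) plus the opposite tail, with SE = SD/√n. For v = 10%, SD = 0.6 and n = 300: ln(1.111) = 0.1054, SE = 0.6/√300 = 0.0346, 0.1054/0.0346 = 3.04, and Φ(3.04 − 1.96) = 0.86.

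| Fall in volume | Change in every concentration | Flagged, SD 0.6, n = 100 | Flagged, SD 0.6, n = 300 | Range, SD 0.4–0.8, n = 100–300 |
|---|---|---|---|---|
| 5% | +5.3% | 14% | 32% | 10% to 60% |
| 10% | +11.1% | 42% | 86% | 26% to over 99% |
| 20% | +25.0% | 96% | over 99% | 80% to over 99% |
| 30% | +42.9% | over 99% | over 99% | 99% or more |

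**Step 3: masking.** If excretion of an electrolyte rises 10% while volume also rises 10%, the concentration ratio is 1.10/1.10 = 1.00 and the raw analysis shows nothing.

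**Step 4: with urine creatinine.** (electrolyte excretion / volume) / (creatinine excretion / volume) = electrolyte excretion / creatinine excretion. Volume cancels. With both excretions constant, the expected ratio to baseline is 1.00 for any *v*, and the test rejects at its nominal 5%. In the masking case, the ratio shows the true 1.10. Fractional excretion is (urine electrolyte × serum creatinine) / (serum electrolyte × urine creatinine). Urine creatinine is the only one of these inputs not already listed.

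**Step 5: with osmolality instead.** Volume cancels here too, but the denominator is total solute. If an electrolyte with its accompanying ions makes up a share *f* of urine solute and its excretion rises by a fraction *g*, the ratio changes by (1 + g)/(1 + f·g), which is less than the true 1 + g. A real change in sodium or potassium is shrunk. A change in any other solute would move all four ratios.

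**The case against.** The strongest reply is that the plan is not blind to dilution. Urine osmolality is itself a laboratory parameter, so Section 9.3.2 already gives its by-visit summary, change from baseline and test. Serum osmolality, BUN, creatinine, weight, and seated and standing blood pressure and pulse also bear on volume status. This stands: a reader might infer that nothing in the study could reveal a dilution shift, and the documents do not support that. But seeing a shift does not say how much of a calcium or sodium change it explains.

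A reader might also infer that a false finding is likely. The documents do not support that either. They give no size or direction for a change in urine concentration on BLI400. Each dose is mixed in 4 to 8 oz of beverage, the dose may be lowered for persistent loose stools (Section 3.4), and some subjects may have used other laxatives up to Visit 1 (exclusion 6). The flag rates above say what the test would do if a shift occurred, not that one will.

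The calcium argument is tempered by Section 1 itself, which says the increased absorption found in animals does not seem to occur in people and that one human study found a decrease. Serum creatinine, eGFR, BUN and urine microscopy also address the kidney. It would be too strong to call urine calcium the decisive marker of a human renal signal.

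Two further replies stand in part. The protocol never calls these values excretion and attaches no decision rule to them; even so, a tested change in urine electrolytes invites that reading. The urine list is open-ended, so the central laboratory might report creatinine; even so, no planned analysis uses it.

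**Conclusion.** The point holds as a cheap improvement to one component of the primary safety endpoint. As written, the plan tests a quantity that mixes dilution with excretion, in a single-arm study of a drug whose action depends on retaining water in the stool. A systematic change in dilution could create or conceal an apparent electrolyte change. If it were a 10% or 20% fall in volume with excretion unchanged, every concentration would rise by 11% or 25%, and the planned comparison could well flag it at this sample size.

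These sizes rest on the assumed volume change, standard deviation and evaluable numbers. That the analysed values are unadjusted concentrations is itself an inference, drawn from the absence of volume and urine creatinine and from the single analysis rule. The documents do not show that a shift will occur or which way it would go. The serum safety tests do not depend on urine dilution, and the osmolality summary gives partial warning.

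**What to change.** Add urine creatinine to the panel in Section 4.1, measured on the existing specimen at every visit. In Section 9.3.2, make the electrolyte/creatinine ratios for sodium, potassium, magnesium and calcium, and fractional excretion from same-visit serum values, the variables analysed for change from Visit 1.

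Keep the raw values in the summary and shift tables, labelled as concentrations, and present them beside the change in urine osmolality.

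Do not make the ratio to osmolality the main adjustment, although it needs no new assay: it assumes constant total solute excretion and can hide real sodium or potassium changes. Use it at most as a labelled sensitivity analysis where urine creatinine is missing.

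The cost is one extra assay per urine sample and a few derived variables, with no new visit or patient procedure. The creatinine ratio has its own limits: it relies on stable creatinine excretion within a subject, and it does not remove true variation in electrolyte excretion by diet or time of day.

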4.1.3. Study Drug

After it has been confirmed that all eligibility criteria have been met, site personnel will utilize the IWRS to assign a drug kit number to the subject.

Site personnel must only dispense the drug kit that has been assigned by the IWRS. Dispensing of incorrect kits is considered a protocol violation.

Subjects will be provided instructions on how to take the study medication and rescue medication. Two bottles will be dispensed per subject. The study drug bottles will be weighed for drug accountability purposes. Subjects will be instructed to return all bottles at each follow up visit.

4.2. Treatment Period

4.2.1. Treatment Day 1

Starting on the morning of Treatment Day 1 (the day after Visit 1), subjects will measure 2 capfuls of study medication and ingest it mixed in a beverage of their choice. Subject will take a daily dose of 2 capfuls until they return for Visit 2. Subjects that develop persistent diarrhea or loose stools should contact their study center. These subjects will be allowed to adjust their dose down to 10.5g (1 capful) per day.

4.2.2. Visit 2 (*Month 2*) +/- 4 days

Subjects will continue to take BLI400 daily and will return to the clinic for Visit 2 (Day 60). Vital signs (see [section 4.1](#) for details) and ECGs will be recorded. Study personnel will weigh returned bottles and count rescue bisacodyl for accountability purposes. Subjects will be queried for any adverse events or changes to their concomitant medications. Subjects will complete the PAC-QOL and PAC-SYM questionnaires. Samples for chemistry, hematology and urinalysis will be repeated as outlined in [Section 4.1](#). Subjects will be dispensed 2 new bottles of study medication. Subjects will be instructed to return all bottles and bisacodyl at the next follow up visit.

